## 5. STUDY CONDUCT

### 5.1. Synoptic diagram of the investigation

For all included patients, the scheduled treatment duration is 12 weeks. Patients will be allocated to the Urgo K2 compression system and a wound dressing from the UrgoStart® range. Both devices must be applied according to manufacturers' recommendations as described in the respective device monographs (Appendix 1&2).

After obtaining the patient's written consent to participate and once all inclusion and exclusion criteria are met, patients will be included in the study. Patients will then be seen at Week 2 and Week 4 ± 3 days during the first month, and then every four weeks, until the 12th week for wound assessment or until complete wound closure if it happens before, with all the visits being documented in the case report form (CRF).

At each of these visits, the investigator will perform a clinical assessment and will measure the wound with a ruler, and will also take a photographic record of the venous leg ulcer.

The treatment may be discontinued, temporarily or definitively, before the required 12 weeks have been completed if the investigator deems this to be necessary: this must be then documented in the Case Report Form (CRF).

A temporary discontinuation of the tested treatment (compression system or the primary dressing) must not exceed 2 weeks; after this time, it will become a permanent discontinuation.

In case of permanent discontinuation, the investigator has to follow-up the patient until Week 12, as expected in the protocol and to treat him at his entire convenience.

The acceptability of the study treatment will also be assessed at each visit planned in the protocol.

## **5.2. INCLUSION VISIT: DAY 0**

Any patient presenting with a new venous leg ulcer (less than six weeks duration) and meeting all the selection criteria may be approached for inclusion in the study irrespective of previous local treatment for his chronic wound.

The patient must be informed of the nature of the study for which he/she is being selected and must sign a written informed consent form in duplicate, prior to any investigation relative to this study.

The investigator then considers that the patient is included in the investigation and must therefore document the Case Report Form.

### **1.2.1. Patient history**

This includes:

- The patient's demographic characteristics,
- The patient's major medical and surgical history (including the comorbidities),
- Current general treatments.

### **1.2.2. Clinical assessment of the patient**

This will be documented in the case report form and includes:

- Peripheral vascular condition, including pulses and ABPI measurement,
- Venous ulcer confirmed by duplex ultrasound scan
- Examination of the leg presenting with the ulcer,
- Number of ulcer(s) of the studied ulcerated limb,
- Ankle circumference.

### **1.2.3. Characteristics of the lesion**

The following will be documented:

- The nature and location of the lesion,
- The clinical status of the wound (presence of sloughy tissue, granulation tissue and necrotic tissue, on the wound bed),
- The condition of the surrounding skin,
- The history of the lesion (duration, recurrence, previous treatment...).

#### **1.2.4. Measurement of the wound**

The surface area of the wound will be measured with a ruler (length and width) and noted in the CRF of the patient.

#### **1.2.5. Photographic record**

Photographs will be taken by the investigator at baseline and at every visit planned in the protocol till the end of the treatment period (Week 12 or before, if withdrawal or healing occurred), according to the investigator's normal procedures.

A ruler will be used when taking the photographic records.

At the end of this Inclusion visit, the investigator will give the Patient a letter for the nurse who will provide the care in the community, between two visits planned in the protocol. This letter will inform the community HCP about the study and will provide recommendations on how to use the products which are under evaluation.

The investigator, at the end of the inclusion visit, will give the patient an appointment for the next visit planned in the protocol, two weeks after the current one.

### **5.3. INTERMEDIATE ASSESSMENT**

Over the 12 weeks of follow-up, intermediate assessments will be performed at the following frequency: W2, W4 and W8.

A period of two week is defined as 14 days ( $\pm 2$  days), which means that:

- W2 is between the 12th and the 16th day of treatment,
- W4 is between the 26th and 30th day of treatment,
- W8 is between the 54th and 58th day of treatment.

At each visit planned in the protocol, the investigator will note the following in the Case Report Form:

- The characteristics of the lesion (if this one is still present),
- The occurrence of any local adverse event (LAE),

**The investigator will also conduct the following:**

- a measurement of the study lesion with a ruler,
- a photographic record of the study lesion.

**The investigator will record the** acceptability of the study procedure, including the following parameters:

- pain level at dressing changes,
- ease of application of the studied procedure (compression and dressing),
- odour, maceration and leakage of exudate,
- assessed qualitatively.

These elements will be documented in the Case Report Form each time a visit is dispensed in the investigating center, at the planned visits.

The investigator, at the end of each of those Intermediate visits will give the patient an appointment for the next visit planned in the protocol, from Week 2 to Week 4 and then after for the following ones, from Week 4 to Week 8 and after, Week 8 to Week 12, which corresponds to the final visit.

#### **5.4. ASSESSMENT IN THE EVENT OF STUDY WITHDRAWAL BEFORE W12**

A premature study withdrawal may occur for any of the following reasons:

- Withdrawal of informed consent,
- Healing of the tested wound; thus, the patient will have to consult the investigator as soon as possible after the onset of the wound closure to document the event and provide the exact date of the closure,
- Onset of a local adverse event requiring permanent discontinuation of the tested treatment,
- Intercurrent adverse event requiring withdrawal,
- Any other reason, to be documented.

A temporary discontinuation of the study treatment must not exceed two weeks; if it does so, it becomes a permanent discontinuation.

**In case of permanent discontinuation of the treatment (studied compression system or the interactive dressing whatever), the investigator is asked to perform the planned protocol evaluations, at the same frequency, until the final evaluation (Week 12), whatever any local treatment applied.**

On the day of permanent discontinuation, the investigator is asked:

- To make a clinical assessment,
- To measure the study lesion with a ruler,
- To make a photographic record,
- To measure the ankle circumference, in order to follow the evolution of any oedema of the lower limb, if existing.

## 5.5. FINAL ASSESSMENT AT THE 12TH WEEK

A complete assessment will be made by the investigator at the 12th week (W12), between the 82nd and 86th day of treatment for all those patients included in the investigation.

This assessment will include:

- A clinical assessment,
- A measurement of the study lesion with a ruler
- A photographic record,
- A measurement of the ankle circumference, in order to follow the evolution of any oedema of the lower limb, if existing.

## 6. ASSESSMENT CRITERIA

### 6.1. MAIN CRITERION

The main judgment criterion is the completely closed study ulcer (100% re-epithelialization) evaluated at last available study visit (12 weeks, at the latest).

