## 2. STUDY OUTCOMES

### 2.1. PRIMARY OUTCOME

The primary endpoint of this clinical investigation is to assess the efficacy of a global treatment for venous leg ulcers, comprising a combination of a multilayer high compression system, UrgoK2® in addition to an interactive dressing, named UrgoStart® Plus (Pad and Border).

The Main efficacy criteria will be complete ulcer closure (100% re-epithelialisation) after a maximum of 12 weeks treatment period.

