### **The occurrence of a local adverse event**

- Does not necessarily represent a reason for premature study withdrawal,
- Leaves the investigator free to continue or to stop the study treatment, either temporarily or definitively, in this case replacing it with a treatment considered to be more appropriate, based on his/her clinician experience,
- Must be documented in the case report form and will be the subject of a clinical, and photographic assessment.

If an adverse event requires the investigator to discontinue definitively the study treatment, this must be documented in the Case Report Form, on the “Early termination before W12”.

Any local adverse event involving the permanent discontinuation of treatment must be reported by the patient and/or the community HCP, to the principal investigator by phone within 48 hours and by email within 3 days.

If the occurrence of a local adverse event leads to a temporary discontinuation of the study treatment, this should not exceed 2 weeks; after that it becomes permanent and the investigator will then have to complete the “Early termination before Week 12” section in the Case Report Form.

The investigator could then document the description of this adverse event and its evolution in a specific materiovigilance document and send it to the manufacturer of the two tested devices ([[contact]](mailto:[contact])).

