#### **10.3.1. Definition of the populations**

The following populations will be studied:

- The Intent to Treat population (ITT) is defined as all patients who received at baseline the allocated studied procedure and for whom a documented ulcer status (at minimum closed or not closed ulcer) is available at least one time after the inclusion of the patient.
- The Per Protocol population (PP) consists of all ITT patients, for whom no major protocol deviations were observed, and have been treated with the allocated procedure for a minimum of 4 weeks.
- The Safety population is defined as all included and treated patients (at least one documented application of studied systems).

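### As written, an ulcer that closes on replacement treatment after a study device is permanently stopped counts towards the closure rate of the UrgoK2/UrgoStart combination

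*Protocol*

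**What the plan says.** Section 2.1 gives the aim of the primary endpoint as "to assess the efficacy of a global treatment for venous leg ulcers", namely UrgoK2 together with UrgoStart Plus. It words the criterion as "complete ulcer closure (100% re-epithelialisation) after a maximum of 12 weeks treatment period". Section 6.1 repeats the criterion and fixes when it is read: "evaluated at last available study visit (12 weeks, at the latest". Neither section says which treatment the patient must be on at that visit.

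Patients who stop a device remain under observation. Section 5.1 states that "the investigator has to follow-up the patient until Week 12, as expected in the protocol and to treat him at his entire convenience". Section 5.4 applies this to a stop of either the compression or the dressing, with the planned evaluations continuing "until the final evaluation (Week 12), whatever any local treatment applied". Section 5.5 requires the Week 12 assessment for every included patient. Section 7 allows the investigator to stop the study treatment after a local adverse event, "replacing it with a treatment considered to be more appropriate".

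Section 10.3.1 keeps in the ITT set anyone who received the procedure at baseline and has at least one later ulcer status. The per-protocol (PP) set takes ITT patients without a major protocol deviation who "have been treated with the allocated procedure for a minimum of 4 weeks".

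**The concern.** The trial has one arm, and its primary result is a single closure proportion presented as the efficacy of a specific pair of devices. If closures reached on other products enter the numerator, that proportion no longer measures only what the pair achieved. In a randomised trial the same scoring would apply to both arms and the comparison would absorb much of its effect. Here there is no comparator, so each such closure can only raise the figure credited to the combination. The poorer the tolerance of the devices, the more room there is for this to happen. The reported rate would not show it, and the listing of discontinued patients in section 10.3.2 does not include closure status.

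**Working it through.** **What the text implies.** The protocol does not state the result in one sentence. It follows from reading the sections in order:

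1. A patient permanently stops UrgoK2 or UrgoStart before closure. Sections 5.1 and 5.4 require the planned evaluations to continue to Week 12, with free choice of treatment.
2. The last available visit of that patient is then normally a visit on replacement treatment.
3. Section 6.1 reads closure at that visit without a condition on treatment. If the ulcer is closed, the patient is a primary success.
4. The ITT definition keeps the patient in the analysis.
5. For the PP set, timing matters. A patient who stops at Week 2 fails the four-week requirement and is removed. A patient who stops at Week 5 meets it, and leaves the PP set only if the stop is classed as a major deviation. The protocol does not say that it is, and its own rules permit discontinuation.

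**Size.** There is no figure in the plan to reproduce. Section 10.1 gives N = 60 without a rate, precision or dropout, and the point does not depend on how 60 was reached. Inputs:

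- N = 60 (sections 1 and 10.1), with all 60 taken to be in the ITT set.
- d, the share permanently discontinuing before closure: not given; assumed 5%, 10% and 20%.
- h, the share of those who close by Week 12 on other treatment: not given; assumed 30% to 60%.

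One closure weighs 1/60 = 1.67 percentage points. The addition to the closure rate is (N × d × h)/N = d × h:

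| d (patients) | h | Closures after discontinuation | Added to the rate |
|---|---|---|---|
| 5% (3) | 30% | 3 × 0.30 = 0.9 | 0.9/60 = 1.5 points |
| 10% (6) | 50% | 6 × 0.50 = 3.0 | 3.0/60 = 5.0 points |
| 20% (12) | 60% | 12 × 0.60 = 7.2 | 7.2/60 = 12.0 points |

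The only closure figure in the protocol is the 30% to 75% at six months in the Introduction. It covers a longer period than a patient has left after stopping within 12 weeks. Taking its upper end, h = 75%, would give 3.8, 7.5 and 15.0 points for the three values of d.

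**Against sampling error.** Exact (Clopper-Pearson) 95% intervals at n = 60 are:

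- 18/60: 18.8% to 43.2%, half-width (43.2 − 18.8)/2 = 12.2 points.
- 30/60: 36.8% to 63.2%, half-width (63.2 − 36.8)/2 = 13.2 points.
- 45/60: 62.1% to 85.3%, half-width (85.3 − 62.1)/2 = 11.6 points.

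At the top of the assumed range the effect is as large as the sampling error. At the bottom it is about the weight of one patient.

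**The case against.** **Reading closure regardless of treatment is legitimate.** It is a treatment-policy estimand, it suits an ITT set that keeps discontinuers, and following everyone to Week 12 is good practice. This stands. A reader might infer that the planned rate is simply biased upward. The documents support that only if the target is closure achieved on the combination. Measured against the rate that would have been seen had everyone stayed on the devices, the direction is unknown.

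**The discontinuation visit may be the last visit.** Section 5.4 lists stops for adverse events under premature study withdrawal, section 7 sends such patients to an early-termination page of the CRF, and Appendix (ix) has a column for termination before Week 12. Section 2.1 also speaks of a treatment period. None of this overrides the explicit instruction in section 5.4 to continue evaluations to Week 12, and section 2.1 does not say that the period ends at discontinuation. If it were read that way, 2.1 and 6.1 would need to be aligned in any case.

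**The SAP may settle it.** A SAP may exist and is not shown. But the protocol itself fixes the primary criterion in 6.1, and a later rule counting these closures as failures would change that criterion rather than add detail to it.

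**The PP set already protects.** It does so in part: it removes those who stop before four weeks, and anyone whose stop is judged a major deviation. A reader might infer that it gives no protection, which is wrong. It is equally wrong to rely on it for stops after Week 4.

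**The remedy has its own distortion.** Scoring discontinuers as not closed is a composite. It counts as not closed a patient who stops for an unrelated reason, or who stops only the dressing and stays in UrgoK2, even if the ulcer then closes. This is true, and it is why both rates should be shown.

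**Conclusion.** The point holds. Followed as written, the protocol counts closures on replacement treatment towards the closure rate of the combination, in a single-arm trial whose stated aim is the efficacy of that combination. The size cannot be known from the protocol: 1.7 points per closure, and about 1.5 to 12 points under assumed discontinuation of 5% to 20% with 30% to 60% closing afterwards. If few patients stop a device, the effect is small.

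A reader might also infer that the trial's whole efficacy evidence is affected, or that a conclusion would be reversed. The documents do not support either. Closure is the primary result but not the only efficacy result: sections 2.2 and 6.2 also list time to closure, area reduction and the proportion with at least 30% reduction at Week 4. Section 10.1 plans no test, and no success threshold is set. What is at stake is the meaning of the headline rate.

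**What to change.** In sections 6.1 and 2.1, add that a success of the combination is a closure documented before permanent discontinuation of either study device. Permanent discontinuation is as sections 5.1 and 5.4 already define it, including the rule that an interruption of more than two weeks becomes permanent. Patients who discontinue before closure are counted as not closed on the combination. Beside this rate, report the closure rate regardless of treatment and the number of closures after discontinuation, in both the ITT and PP sets. Keep the Week 12 follow-up and all care rules unchanged.

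The cost is a sentence in each section and one extra line in the results table. The data are already collected: discontinuation is recorded in the CRF, section 5.4 requires an assessment on the day of permanent discontinuation, and it asks for the exact date of closure. The downside is a somewhat lower headline rate. Some patients who stop for reasons unrelated to the devices will count as not closed, which the rate regardless of treatment makes visible.

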### 6.2. SECONDARY CRITERIA

The secondary criteria are to assess or to measure the:

- Time to reach complete wound closure,
- Relative and Absolute wound surface area reduction ( $\text{area}_{t0} - \text{area}_{t\text{last}}$ ),
- Percentage of patients with a  $\geq 30\%$  wound area reduction  $[(\text{area}_{t0} - \text{area}_{t\text{last}}) / \text{area}_{t0} * 100]$  at Week 4,
- Evolution of the ankle circumference,
- The Patient Quality of Life through a specific the WoundQuol Questionnaire,
- The safety of the procedure (nature and number of emergent local adverse events),
- Patients' acceptability to the studied procedure (compression system and dressing) evaluated by the investigator and by the patient,
- The dressing change frequency.

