**APPENDIX (ix)****SYNOPSIS OF THE CLINICAL TRIAL**

	Inclusion visit Day 0	Follow-up visits W2 / Week 4 / Week 8	Termination before W12, whatever reason	End of the study or Week 12
INVESTIGATOR				
Informed consent	X	-	-	-
Inclusion criteria validation	X	-	-	-
Exclusion Criteria validation	X	-	-	-
Ankle Brachial Pressure Index Vascular Assessment	X*	-	-	-
Wound clinical assessment	X	X	X	X
Measurement of the Wound	X	X	X	X
Photographic record	X	X	X**	X**
PATIENT				
Acceptability	-	X	X	X
Quality of Life Questionnaire	X	-	X	X

*\*ABPI to be assessed at baseline if not available in the 3 previous months.*

*\*\*A photographic record of the treated ulcer will be taken also in case of occurrence of a local adverse event.*

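### Ankle circumference is a secondary endpoint, but the visit schedule omits it and the protocol conflicts on whether patients healed before Week 12 give an end value

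*Protocol*

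**What the plan says.** **Endpoint.** Protocol sections 2.2 and 6.2 both list "Evolution of the ankle circumference" among the secondary criteria.

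**Where the body text requires it.**
- Day 0: "Ankle circumference" is the last item of the patient's clinical assessment under section 5.2 (subsection numbered 1.2.2).
- Early stop: section 5.4 has a procedure list that includes the ankle, introduced by "On the day of permanent discontinuation, the investigator is asked".
- Week 12: section 5.5 lists "A measurement of the ankle circumference, in order to follow the evolution of any oedema of the lower limb, if existing" and addresses the assessment to every included patient.

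**Where it is not named.**
- Section 5.1, on the follow-up visits: "At each of these visits, the investigator will perform a clinical assessment and will measure the wound with a ruler", plus a photograph.
- Section 5.3, for Weeks 2, 4 and 8: "a measurement of the study lesion with a ruler", a photograph, lesion characteristics, local adverse events and acceptability.
- Appendix (ix): there are rows such as "Ankle Brachial Pressure Index Vascular Assessment" and "Measurement of the Wound", and rows for photographs, acceptability and quality of life. No column has an ankle entry, including Day 0, early termination for any reason, and Week 12.

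**Healed patients.** Section 5.1 runs visits to Week 12 or to closure, whichever comes first. Section 5.4 lists healing as a reason for premature study withdrawal and asks the patient to attend so that the closure and its date can be documented.

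**The concern.** A change score needs a start value and an end value. Every patient should have the start value. For patients who heal before Week 12, the end value depends on which section the site follows. If they leave at closure unmeasured, the missing values are determined by the primary outcome itself, and the summary of ankle change would rest mainly on ulcers that did not close. The descriptive summaries in section 10.3 cannot correct this, and a later analysis plan cannot recover a measurement that was never taken.

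The schedule table adds to the risk. Its early-termination column would catch healed patients, but it does not prompt for the ankle.

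**Working it through.** **Step 1: set the sections side by side for a patient who heals before Week 12.**

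| Section | What happens to the patient | Ankle measured? |
|---|---|---|
| 5.1 | Visits end at closure | Not named |
| 5.4, withdrawal reasons | Healing is a withdrawal; the visit documents closure and date | Not named |
| 5.4, procedure list | Applies on the day of permanent discontinuation; not said whether a healing exit counts | Yes, if it counts |
| 5.5 | Week 12 assessment of every included patient | Yes |
| Appendix (ix), early-termination column | Applies whatever the reason | No row |

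Two other places point towards exit at closure. The photographic record subsection of 5.2 lets photographs stop at healing, and section 6.1 judges the main criterion at the last visit on record, Week 12 at the latest. Section 5.4 also tells the site to continue protocol evaluations to Week 12 after a permanent discontinuation, which sits badly with a healed patient whose visits end under 5.1. So exit without a measurement is a plausible reading, but not the only one.

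**Step 2: inputs for the size.**
- N = 60 (section 1). The protocol gives no precision target and no figure for this endpoint, so there is no stated result to reproduce.
- h, the share healed before Week 12: not given. The only healing range in the document is 30–75% at six months (Introduction). It is borrowed here as an assumption, with 50% as a point within the range.
- D, the absolute difference in mean ankle change between healers and non-healers: not given. Assumed 0.5 to 2.0 cm.

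**Step 3: formulas, if no early healer has an end value.**
- Patients contributing: n = 60 × (1 − h).
- The full mean is h × (healer mean) + (1 − h) × (non-healer mean), and the reported mean is the non-healer mean alone. The shift therefore has size h × D.
- Standard error relative to all 60 measured, assuming a common standard deviation: √(60/n).

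**Step 4: results.**

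| h (assumed) | n contributing | SE multiplier | Shift, D = 0.5 cm | Shift, D = 1 cm | Shift, D = 2 cm |
|---|---|---|---|---|---|
| 30% | 60 × 0.70 = 42 | √(60/42) = 1.20 | 0.15 cm | 0.30 cm | 0.60 cm |
| 50% | 60 × 0.50 = 30 | √(60/30) = 1.41 | 0.25 cm | 0.50 cm | 1.00 cm |
| 75% | 60 × 0.25 = 15 | √(60/15) = 2.00 | 0.38 cm | 0.75 cm | 1.50 cm |

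**Step 5: the other reading.** If section 5.5 is applied as written, all 60 patients are due a Week 12 value. Then n = 60, the multiplier is 1 and the shift is zero.

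**The case against.** A reader might infer that the protocol requires no end value from healed patients, so that the endpoint is by design estimated in non-healers. The documents do not support that. Section 5.5 exempts nobody. Section 5.4 is about withdrawal before Week 12, names healing among the reasons, and its only procedure list includes the ankle; since a healed patient has stopped the study dressing for good, that list can be read to cover a healing exit. This part of the objection stands: the defect is a conflict between sections, and the selective loss of data is a risk under one reading.

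A reader might also infer that sites working from Appendix (ix) would collect no ankle data at all. That goes too far. The appendix is a synopsis; it also leaves out demographics, medical history, the duplex scan and adverse events, all of which the body requires, and nothing says that it overrides the body. The missing row is still an inconsistency for a named endpoint.

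On Weeks 2, 4 and 8, a start and an end value can satisfy a change endpoint, and the protocol states no aim about early oedema loss. Leaving these visits out is therefore a design choice. Section 5.1 does call for a clinical assessment at each visit, and at Day 0 the ankle falls under that heading. But 5.4 and 5.5 list the two separately, so this does not settle the matter.

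Finally, the centimetre figures rest on assumed inputs, and this is one of eight secondary criteria in a single-arm study summarised without tests. Both remarks are fair and limit the severity.

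**Conclusion.** The concern holds in a limited form. Ankle circumference is a stated secondary endpoint with no row in the visit schedule and no mention at the intermediate visits, and sections 5.1, 5.4 and 5.5 do not agree on whether a patient healed before Week 12 provides an end value.

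The possible effect runs from none, if 5.5 is followed literally, to a shift of 0.15–1.5 cm in the reported mean change with 42 down to 15 of 60 patients contributing, if every early healer leaves unmeasured. That range assumes 30–75% healed (a six-month range borrowed for 12 weeks) and a 0.5–2 cm difference for which the protocol offers no data. The direction is unknown. The figures show why the text should be settled; they do not predict the bias. The primary outcome is unaffected. Severity is minor to moderate.

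**What to change.** 1. Reconcile sections 5.1, 5.4, 5.5 and Appendix (ix) so that they give one answer on whether patients healed before Week 12 return for the Week 12 assessment.
2. State in section 5.4 that ankle circumference is measured at the closure visit, as well as on the day of permanent discontinuation and at Week 12.
3. Add an ankle-circumference row to Appendix (ix), marked at Day 0, at termination for any reason including closure, and at Week 12.
4. Optional: add the measurement to the section 5.3 list for Weeks 2, 4 and 8, which would show the course over time.

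The cost is one tape measurement and one case report form line at visits that already take place, plus the wording change. If closure values serve as end values, they will fall at different times after Day 0, so the report should give the timing alongside the change.
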